### 7.8.1. Explantation of VC-02-20TM Sentinel Units

All sentinel units will be explanted at time-points to be determined by the Sponsor (refer to the Schedule of Assessments). In both Cohort 1, up to ten (10) VC-02-20 sentinels and in Cohort 2, up to twelve (12) VC-02-20 sentinels may be implanted in a subject. The number of sentinels implanted will be determined by the Sponsor in collaboration with the Investigator and Surgeon. The decision will be based on the available data from previous subjects as well as on the availability of anatomical space for surgical implantation.

### 7.8.2. Explantation of VC-02-300™ Units

As outlined in the Schedule of Assessments, VC-02-300 units will be removed from all subjects at the end of the specified treatment period or earlier if the subject wishes to withdraw from the study, has a safety event which requires explant, or if the Sponsor, Ethics Committee, DSMB, or Regulatory Authorities stop the study.

At the discretion of the Sponsor and after consultation with the Investigator, or if a unit is suspected to be malfunctioning or damaged, explantation of the section of the subject. Explant of the subject is allowed at any time post-occur without requiring the subject to officially withdraw from the study (Section 13.6). Although the sentinel units implanted in subjects are expected to behave similarly to the VC-02-300 units,

will provide additional data on the status of graft function and cell performance.

# 7.9. Histological Assessment of VC-02 Combination Product

All explanted VC-02-20 sentinels and VC-02-300 units will be placed immediately in a fixative solution and shipped to the Sponsor for histologic assessment. Explant preparation and shipping instructions will be provided to each site. Systematic, histologic evaluation of sentinel explants will help inform the Sponsor as to the expected performance of the larger VC-02-300 units while the study is ongoing. Histological assessment of the units will be performed by the Sponsor or designee and may include but is not limited to:

Data from this evaluation may be captured in a separate database and described in a separate study report. The data may be used to optimize the surgical procedures and technique, the anatomical location of implants, or the perioperative care associated with VC-02. Results from these assessments may be compared to the Sponsor's database

## 7.10. Blood Glucose Monitoring

Throughout the trial, the exogenous insulin requirements of enrolled subjects are managed and titrated by the Investigator (or qualified designee) as needed to maintain glycemic control in conjunction with standards of care. For purposes of this study, the diary entries made by the subjects (e.g., insulin doses, SMBG values, and HE occurrences) are the main sources of information available to the Investigator to assist with treatment decisions. CGM data may be utilized for treatment decisions in accordance with local labeling market approvals.

In addition to Investigator review of glucose trends, insulin dosing, and HE occurrences, the Sponsor will conduct routine reviews of blood glucose data. These data are collected as part of the required study procedures. Subjects record insulin dosing and all HE occurrences on a study diary and glucometer data are electronically downloaded. The data are then available in near real-time for review. If potentially concerning trends are evidenced for an individual subject, the Sponsor will notify the Investigator and request for follow-up with the subject to occur if necessary.

Blood glucose monitoring is performed through various methods during the study to ensure proper glucose control:

- Laboratory tests (Sections 7.2, 7.3, and 7.11)
- Continuous Glucose Monitoring (Section 7.10.2)
- Self-Monitoring Blood Glucose (Section 7.10.3)

Data from these methods will be available to the Investigator via reports from laboratories, study diaries, and downloads or entries from CGM and SMBG meters to facilitate treatment decisions. The glucose monitoring data collected between Visit 2 (Week -4) and Visit 3 (Day 1) establishes the baseline profile of each subject's glycemic control (e.g., the percent time spent at various blood glucose cutpoints per CGM data, SMBG blood glucose levels, exogenous insulin doses, and frequency of HEs).

During the study, decreasing requirements for exogenous insulin may be achieved gradually as cells differentiate into mature, insulin-secreting cells. This reduction in exogenous insulin dose typically is expected to occur over a period of three (3) to six (6) months post-implantation, but may occur later in some patients. In addition to the requirement for frequent review of the available sources of subject-reported data, Investigators are encouraged to engage in routine contact with subjects (e.g., phone calls, texts, and emails) and/or schedule Unplanned Visits between the

18 MAY 2020

A study reference manual may further outline the various logs and data collection portals available to the Investigator.

## 7.10.1. Study Diary

Starting at Visit 2 (Week -4) and throughout the duration of participation in the trial, subjects are required to enter or download all SMBG values, HE occurrences and associated symptoms, and insulin doses into the study diary on a daily basis. Because treatment decisions are based, in part, on the availability of this information, the Investigator must make all reasonable efforts to ensure subjects comply with the requirement for daily entry of this important information. After implantation, if a subject demonstrates repeated non-compliance with this requirement, the Investigator must document efforts to correct and prevent future non-compliance in the subject source records.

At a minimum, diary data must be reviewed by the Investigator at each study visit to determine if insulin dosing should be modified. Review of available study diary data at each visit must be documented in the subject source records. Subject diary entries may also be available for review in near real-time by the Investigator using secure cloud technology, and automated e-mail alerts may be configured for alert to the Investigator for occurrences of potential safety-related issues (e.g., if a SHE is reported or if the frequency of HEs reported within a certain period requires further evaluation).

## 7.10.2. Continuous Glucose Monitoring (CGM)

All subjects will be provided with a CGM system. Previous experience with CGM is not a requirement of study entry, but all subjects are required to use the Sponsor-provided CGM during study participation. Based on the labeled indication of the CGM in use, diabetes treatment decisions may be based on CGM data collected. Subjects relying on CGM data for treatment decisions will be required to be compliant with CGM usage and wear the CGM for the entire two-year study and also periodically sync the data, so that near-real time access may be available to the Investigator and Sponsor. A study reference manual will further outline the logistics with respect to CGM use and data collection.

All CGM supplies and instruction manuals will be provided by the Sponsor. Site personnel will instruct the subject on proper use and care at Visit 2 (Week -4) and as needed throughout the study. This training includes assisting the subject with the insertion of the first sensor needle prior to leaving the clinic at Visit 2. The CGM system is configured to alert the subject in the event blood glucose values approach hypoglycemic levels.

The CGM data collected for this trial will be used to evaluate secondary and exploratory endpoints. Data from the two weeks prior to appropriate clinic visits will be used in order to calculate the CGM endpoints (e.g., percent of time a subject's blood sugar is <54 mg/dL,  $\geq 54 \text{ to } <70 \text{ mg/dL}$ ,  $\geq 70 \text{ mg/dL}$ , and >180 mg/dL). Other endpoints using CGM data may be evaluated and, if so, will be described in the Statistical Analysis Plan (SAP).

#### 7.10.3. Self-monitoring Blood Glucose (SMBG)

SMBG supplies including a Sponsor-provided portable meter, test strips, lancets, control solution, and sharps containers will be provided and required for use by each subject starting at Visit 2 (Week -4). Instructions for routine SMBG monitoring via fingerstick and calibration of the meter will be provided to each subject. The recommended frequency of SMBG monitoring will be determined for each subject by the Investigator. All SMBG values, whether conducted for routine blood glucose monitoring, confirmation of hyperglycemia or hypoglycemia, or due to the calibration requirements of the CGM equipment, will be logged on a study diary.

### 7.10.4. Definition, Classification, and Management of Hypoglycemic Events (HEs)

All SMBG or CGM values of <54 mg/dL must be captured by the subject in the diary as a HE. Additionally, if a subject does not have a blood glucose value available, but has symptoms of a HE, the HE must still be captured in the diary as an HE. *For any SHE experienced between scheduled clinic visits, the subject must enter the data on the diary and also contact the study site to provide details of the event.* 

At Visit 3 (Day 1) and each clinic visit thereafter, the Investigator will review the subject's HE entries on the study diary, CGM and SMBG values, and any other supportive information. Each HE occurring beyond Visit 2 (Week -4) must be captured on a CRF and will be classified based on the definitions below. Per standards of care, the Investigator should also evaluate any HEs occurring between Visit 1 and Visit 2 reported by the subject, but they are not captured on the CRF.

- Severe hypoglycemic event (SHE): an event requiring assistance of another person to actively administer carbohydrate, glucagon, or other resuscitative actions.
- Documented symptomatic hypoglycemia: an event accompanied by typical symptoms of hypoglycemia with documented plasma glucose measured at <70 mg/dL (3.9 mmol/L).
- Asymptomatic hypoglycemia: an event with measured plasma glucose of <54 mg/dL (3.0 mmol/L) in the absence of symptoms.
- Probable symptomatic hypoglycemia: subject reports typical hypoglycemia symptoms but does not provide a temporally-associated SMBG or CGM value.
- Pseudo-hypoglycemia or relative hypoglycemia: an event is reported by subject, but the associated SMBG or CGM value is ≥70 mg/dL (3.9 mmol/L).

The frequency of HEs will be captured and counted over the course of the study. In addition, the Sponsor will consider defining additional HEs using the CGM data on an exploratory basis. The Investigator may request an Unplanned Visit to review study diary entries and determine if modifications in insulin dosing are necessary to reduce the occurrence of HEs. Based on available information, the Investigator should make appropriate decisions regarding the insulin therapy to mitigate HE occurrences.

## 7.11. Laboratory Evaluations

Central laboratories identified by the Sponsor will test the majority of protocol-required, biological samples collected from subjects in the study. Details regarding the laboratory specimen preparation, handling, storage, shipping and reporting procedures will be outlined in a separate laboratory reference manual. All protocol-required samples will be collected at the time-points indicated on the Schedule of Assessments.

As needed (e.g., immunosuppression drug levels, absolute lymphocyte counts [to confirm adequate pre-implant immunosuppression has been achieved], or urgent medical events), local laboratories available to a site may be utilized.

All laboratory test results outside of normal range should be evaluated by the Investigator for any clinical significance and addressed in accordance with standards of care. The Investigator may order repeat tests once for additional evaluation of potentially significant results. The Sponsor should be contacted if additional testing is required after repeat tests have been conducted.

### 7.11.1. Routine Clinical Laboratory Evaluations

Subjects will have routine laboratory assessments performed throughout the study, including:

- Hematology: hemoglobin, hematocrit, RBC count, platelet count, WBC count, total neutrophils, eosinophils, monocytes, basophils, and lymphocytes.
- Chemistry: BUN, serum creatinine, total calcium, sodium, potassium, chloride, bicarbonate, magnesium, phosphate, uric acid, ALT, AST, LDH, alkaline phosphatase, total bilirubin (direct and indirect bilirubin reflexively measured only when total bilirubin is greater than the ULN), creatine phosphokinase, albumin, and total protein.

If a subject demonstrates an ALT and/or AST values of >3 x ULN during the study, the subject will re-test every five to seven days until the values return to <3 x ULN. An ALT or AST value of >3 x ULN with total bilirubin  $\ge$ 2 x ULN and alkaline phosphatase <2 x ULN will require re-testing every three to five days.

- Fasting serum lipid panel: total cholesterol, HDL-C, calculated LDL-C (Friedwald), triglycerides, VLDL. Non-HDL-C will be calculated as TC HDL-C. When triglycerides are >400 mg/dL, another sample will need to be collected from the subject and a directly measured LDL will be done.
- Urinalysis (central lab dipstick): pH, protein, blood, ketones, leukocyte esterase, and nitrites. Microscopy is done if the dipstick sample is positive for blood, nitrites, leukocytes, and/or protein. A bacterial culture and sensitivity will be done if nitrites or leukocyte esterase are positive. Another sample will need to be collected from the subject and submitted in order to perform the culture and sensitivity testing.

At visits where a urine albumin/creatinine ratio is performed, the determination must be made on the first morning void.

• Serology: screening for HB core and sAg/Ab, HCV, HIV (1&2), CMV IgG, and EBV IgG. Subjects are also tested post-implant via CMV PCR at Weeks 12 and 26. Additional CMV

IgG and IgM testing is completed at Week 52 and Week 104 *only if previous CMV testing was negative*.

• Other: HbA1C, ultrasensitive C-peptide (collected in conjunction with MMTTs prestimulation (time = 0) and post-stimulation at a 90 minute [+/- 10 minutes] timepoint), urine pregnancy tests, Quantiferon, renal function evaluation via MDRD eGFR calculation, and TSH (screening).

#### 7.11.2. **Pregnancy Tests**

A urine pregnancy test is administered to all women at Visit 1 (Week -5), at Visit 3 (pre-implant), and post-implant at Visit 13 (Week 52) and Visit 17 (Week 104) or early termination. However, additional pregnancy tests may be completed if the Investigator suspects a possible pregnancy, as per request of the Ethics Committee, or if required by local regulations.

#### 7.11.3. Immunosuppression Drug Levels and Safety Labs

Certain drugs prescribed as part of each subject's immunosuppressive regimen may require additional blood testing to ensure appropriate concentrations are achieved to facilitate the engraftment and long-term function of implanted VC-02 units. Routine testing of concentration levels is required to avoid drug toxicity and any associated adverse events. Refer to Section 5.2 for details on the planned immunosuppression regimen.

Based on the immunosuppression regimen prescribed for the patient, and after discussions between the Sponsor and Investigator, the target concentration of each applicable drug, as well as the frequency of any additional blood testing required to obtain concentration results and assess safety (e.g., additional hematology and chemistry testing), will be included as part of the implantation strategy plan for the subject. Blood collections required to measure immunosuppression drug levels may be collected at regularly scheduled protocol visits or at an Unplanned Visit as needed, depending on the frequency of the required drug concentration monitoring.

### 7.11.4. Immune Panel

Blood samples for humoral and cellular immunity testing will be obtained at specific time-points throughout the trial as listed in the Schedule of Assessments. The panel of immune function tests includes those listed below:

Blood samples will be sent to a central or third-party lab with results sent to ViaCyte for possible inclusion in the clinical study database. The results of these tests will help inform ViaCyte's

research and may not be provided to the clinical sites. If there is enough of a blood sample remaining on the collected samples, other immune function related tests may be performed, but no additional blood collection would be required. Fasting is not required prior to collection of these samples.

The cellular allo- and autoimmunity blood samples require additional processing prior to analysis that must be initiated within 24 hours of the collection time. If the additional processing cannot be completed onsite before being sent to the central laboratory, collection of the samples must occur during specific hours to maintain stability of the sample. If needed, these samples can be collected on a day prior to the remainder of the visit in order to meet the stability requirements, but within the protocol-allowed visit windows. The baseline sample may be collected at any time between Visit 2 and Visit 3 once determined the subject qualifies for the study. Additional details are provided in a separate laboratory manual.

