## 5.2. Immunosuppression Medications

An immunosuppressive regimen will be prescribed for each subject to facilitate the engraftment and long-term function of implanted VC-02 units. The overall regimen may include the following agents (\**Day 1 is Implant Day*):

- Induction (Cohort 1)
  - Basiliximab: Recommended course of 20 mg IV on Day 1 and Day 5. However, it may be administered as early as Visit 2 (Week -4).
- Induction (Cohort 2)

If data collected from Cohort 1 indicate sufficient engraftment and cell viability is achieved with basiliximab, its use will continue in Cohort 2. However, if data from Cohort 1 and/or data collected in subsequent subjects in Cohort 2 indicate insufficient cell viability is achieved, the following agent may be utilized:

- Anti-thymocyte globulin (ATG) recommended course:
  - Day -2 (0.5 mg/kg IV) required dose
  - Day -1 (1.0 mg/kg IV) required dose
  - Day 1 (1.5 mg/kg IV) required dose
  - Up to two additional 1.5 mg/kg/day IV doses of ATG may be administered (on Day 2, and/or Day 3). Prior to any additional dose administration of ATG, an absolute lymphocyte count (ALC) will be obtained locally. If the ALC has been reduced by at least 90% versus the pre-ATG administration level, additional dose(s) of ATG may not be required. The Investigator should contact the Sponsor to determine the need for additional dosing.

However, ATG may be administered using the above dosing schedule as early as Visit 2 (Week -4).

• Maintenance (both Cohorts)

The starting doses and target serum trough concentration levels listed below are recommendations. As determined by the Investigator and after consultation with the Sponsor, the doses and target trough levels may be adjusted.

- Mycophenolate mofetil (MMF): Recommended starting dose of 1 gm PO BID as early as Visit 2 (Week -4). Adjust the dose downward for gastrointestinal side effects. Mycophenolic acid (Myfortic) may be taken alternatively to alleviate such side effects. Trough level measurements for MMF are not required.
- Tacrolimus:

- If combined with MMF: Recommended starting dose of 2 mg PO BID as early as Visit 2 (Week -4); target serum trough concentration level of 10-12 ng/mL during the first three (3) months. Adjust the dose to maintain a serum trough concentration level of 7-9 ng/mL thereafter. Serum creatinine values should also be collected in conjunction with Tacrolimus trough levels in order to monitor for potential renal toxicity.

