# 6.2. Visit 2 / Screening (Week -4 to Week -2)

Subjects meeting eligibility criteria will return for Screening Visit 2 (Week -4). Subjects must be fasted for this visit. The following procedures will be completed:

- Review and confirm continued eligibility criteria.
- Obtain weight/vitals.
- Obtain all laboratory samples per the Schedule of Assessments.

*Note*: The immune panel blood samples may be collected at any time between Visit 2 and Visit 3, once the subject's study qualification is confirmed (Section 7.11.4).

• Perform the 4-hour MMTT. This is the baseline MMTT for efficacy evaluations.

- Dispense Continuous Glucose Monitoring (CGM) equipment and provide instructions. Insert the first sensor at the clinic. Confirm the CGM is functioning prior to the subject leaving the clinic.
- Dispense Self-Monitoring Blood Glucose (SMBG) equipment and provide instructions. Use of the meter provided by the Sponsor is required.
- Dispense the study diary and provide instructions. This is where the subject will capture insulin doses, details on HEs, and SMBG values. Remind the subject that eligibility for the trial requires daily compliance with entries between Visit 2 and 3.
- Dispense immunosuppression drugs and provide instructions for dosing (as needed).
- Assess AEs and concomitant medications.
- Contact the Sponsor to report any schedule changes or updates to the implant date.

The expected duration of the Screening Period is up to approximately five weeks. If the Enrollment Visit 3 is scheduled to occur beyond six weeks (>42 days) from the occurrence of Screening Visit 1, sites must contact the Sponsor before proceeding. Depending on the expected duration of the delay in conducting Visit 3, an Unscheduled Visit may be required to repeat certain screening procedures.

The overall Screening Period may be accelerated, but a minimum of two weeks must elapse between Visit 2 and Visit 3.

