#### 4.3 Assessment Windows

For the purpose of analyzing time to event endpoints, the time-in-study for each subject will be measured relative to Day 1, the day that the surgical procedure for VC-02-300 and/or sentinel unit implantation was attempted.

Study Visit	Target Study Day of Visit	SAP Windows		
Scheduled Study Visits for Cohort 1 and Cohort 2				
Week -4	-29	Day -36 to Day -23		
Week -3	-22	Day -22 to Day -1		
Day 1	1	Day 1		
Day 2	2	Day 2 to Day 3		
Week 2	15	Day 4 to Day 21		
Week 4	29	Day 22 to Day 42		
Week 8	57	Day 43 to Day 70		
Week 12	85	Day 71 to Day 98		
Week 16 (Cohort 1 Only)	113	Day 99 to Day 117		
Week 16 (Cohort 2 Only)	113	Day 99 to Day 126		
Week 17 (Follow-Up		Day 118 to Day 118+		
Visit: Cohort 1 Only)	120			
	Scheduled Study Visits for Col	nort 2 Only		
Week 20	141	Day 127 to Day 161		
Week 26	183	Day 162 to Day 228		
Week 39	274	Day 229 to Day 319		
Week 52	365	Day 320 to Day 410		
Week 65	456	Day 411 to Day 501		
Week 78	547	Day 502 to Day 592		
Week 91	638	Day 593 to Day 683		
Week 104	729	Day 684 to ∞		
Week 105 (Follow-Up Visit)	Last Date of Explantation + 7 Days	Not applicable		

Study visits will have windows as per the following schema:

The data will be summarized based on the electronic case report form (eCRF) (Study Visit) in which it was collected as long as the data is within the windows specified. If data for a particular Study Visit is not within the windows specified, then queries will be sent to the site to confirm data entry. ViaCyte will be notified of Study Visits that are not within the Study Visit Statistical Analysis Plan (SAP) windows. Data collected as an unscheduled visit will be re-assigned to a Study Visit based on the SAP visit windows specified.

Baseline will be defined as the last non-missing value prior to the start time of the surgical procedure for VC-02-300 and/or sentinel unit implantation, unless otherwise specified.

If more than one assessment exists within a single visit window (i.e., vital signs, laboratory samples, etc.), then the value taken closest to the target day of that visit will be used for analysis and summary purposes. In cases where two assessments are equally close to the target day, then

the first value will be used for analysis. Data from all assessments will be provided in the listing.

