#### 7.3.7 Immune Panel

A listing of immune panel tests will be provided. The panel of immune function tests include:

- Humoral alloreactivity measured via human leukocyte antigen panel reactive antibody (HLA-PRA)
- Humoral autoimmunity measured via T1DM autoantibody titers of glutamate decarboxylase antibodies (GADA), insulin antibodies (IAA), islet antigen-2 antibodies (IA2A), and zinc transporter 8 (ZnT8)
- Cellular alloreactivity measured via mixed lymphocyte reaction (MLR)
- Cellular autoimmunity measured via lymphocyte stimulation test (LST)
- Cellular autoimmunity measured via Diab-Q Kit
- HLA typing of each subject (required to interpret the cellular immunity test results)

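### The baseline immune panel is not required to precede the first immunosuppressant dose, so it may be pre-drug in some subjects and on-drug in others

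*Protocol*

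**What the plan says.** **Collection window.** Protocol 6.2 notes that "The immune panel blood samples may be collected at any time between Visit 2 and Visit 3", once qualification is confirmed, and Protocol 7.11.4 repeats the rule: "The baseline sample may be collected at any time between Visit 2 and Visit 3 once determined the subject qualifies for the study". Table 1 places the one pre-implant panel at Visit 2 and the next at Week 4.

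**Drug start.** Protocol 5.2 recommends basiliximab, the Cohort 1 induction agent, on Day 1 and Day 5, then adds: "However, it may be administered as early as Visit 2 (Week -4"). For Cohort 2, ATG may be used if the data show insufficient cell viability. Its recommended course opens with "Day -2 (0.5 mg/kg IV) required dose", followed by required doses on Day -1 and Day 1, but "ATG may be administered using the above dosing schedule as early as Visit 2 (Week -4"). MMF, tacrolimus combined with MMF, and sirolimus may also start as early as Visit 2. Sirolimus is to reach its pre-implant trough by at least Week -2. Protocol 6.2 has drugs dispensed at Visit 2 as needed.

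**Baseline rule.** SAP 4.3 states: "Baseline will be defined as the last non-missing value prior to the start time of the surgical procedure", unless otherwise specified. SAP 7.3.7 specifies nothing different for the immune panel and plans a listing. The panel includes "Cellular alloreactivity measured via mixed lymphocyte reaction (MLR"), a lymphocyte stimulation test (LST), the Diab-Q Kit and HLA panel reactive antibody.

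**The concern.** Immunosuppressants act directly on what this panel measures. A baseline is useful only if it represents the same state in every subject, or if the state is recorded so that it can be allowed for. Here the sampling window and the permitted drug-start window cover the same interval, and no rule orders one against the other.

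The qualification condition can only push the draw later. Some eligibility checks are still open at Visit 2: the stimulated C-peptide exclusion covers the whole screening period, and diary compliance is judged between Visits 2 and 3. A site waiting for these may well draw the panel after drug has begun.

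At stake is the exploratory objective, shared by both cohorts, of assessing the host immune response to the implant. If one subject's MLR, LST or Diab-Q result is compared with a pre-drug sample and another's with an on-drug sample, differences in change from baseline partly reflect when the drug started. A missed pre-drug sample cannot be recovered later.

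**Working it through.** The documents give no figure on this point, so there is nothing to reproduce. The check is day arithmetic on the permitted windows.

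**Inputs**
- Collection window: Visit 2 to Visit 3 (Protocol 6.2, 7.11.4).
- Window length: nominally Week -4 to Day 1, 28 days. The minimum allowed gap is two weeks, 14 days (Protocol 6.2).
- Drug starts: as listed in Protocol 5.2. The ATG course runs Day -2, Day -1, Day 1, so Day -2 is 2 days before Day 1.

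**Formula:** share of window after exposure begins = days from first exposure to Visit 3 ÷ days from Visit 2 to Visit 3.

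| Regimen | 28-day window | 14-day window |
|---|---|---|
| Any agent started at Visit 2 | 28/28 = 100% | 14/14 = 100% |
| Sirolimus at target by Week -2 | at least 14/28 = 50% | 14/14 = 100% |
| ATG on recommended Day -2 start, nothing earlier | 2/28 = 7% | 2/14 = 14% |
| Basiliximab first given on Day 1, nothing earlier | 0/28 = 0% | 0/14 = 0% |

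These are shares of the permitted window, not proportions of subjects. The documents do not say when panels will in practice be drawn or how many subjects will start drug early.

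**Is there an ordering rule elsewhere?**
- The procedure order in Protocol 6 puts blood samples before implantation but does not mention immunosuppressant dosing.
- SAP 4.3 anchors baseline to surgery, not to induction. With one scheduled pre-implant panel it usually has only that sample to use. If a second were drawn, it would select the later one.
- SAP 4.6.3, 4.6.4, 4.6.6.1 and 4.6.7 count the hypoglycemia, CGM and insulin baselines back from Day -3 through Day -30 (30 - 3 + 1 = 28 days), and describe Day -3 as the day before induction. That protects the glycemic baselines against ATG on its recommended schedule. The immune panel has no equivalent.

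**The case against.** The strongest objection is that post-implant panels are themselves drawn on maintenance drug. A pre-drug baseline therefore mixes the effect of the drugs with the effect of the implant, and an on-drug baseline might be the closer comparator. The first part stands and limits what any change from baseline can show. It does not defend the current rule, which fixes neither state. Regimens and start dates vary between subjects, so before first dose is the one reference that can be defined identically for all of them.

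Other limits also stand:
- The overlap is permitted, not certain. A Visit 2 draw before dosing is clean, as is a pre-dose Day 1 draw when basiliximab is the first agent given.
- ATG is conditional and belongs to Cohort 2 only.
- SAP 7.3.7 plans a listing of the panel. SAP 7 adds narratives for confirmed sensitization and says assay data may be summarized.
- Protocol 7.11.4 refers to a laboratory manual that was not available and could contain a restriction. Protocol text allowing any time in the window would then have to be reconciled with it.

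A reader might infer more than this in three ways.

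1. **That a post-ATG baseline reflects 10% or less of usual lymphocytes.** Protocol 5.2 does say "If the ALC has been reduced by at least 90% versus the pre-ATG administration level", but this is the point at which additional doses may not be needed. It is checked before the optional Day 2 and Day 3 doses, after the three required ones. It is neither a target nor a count expected on Day -1 or Day 1, and no lymphocyte figure is given for those days.
2. **That later recovery would be mistaken for a response to VC-02.** This is possible, but with maintenance drug continuing after implant, the documents do not establish the direction.
3. **That the Cohort 1 sensitization endpoint is undermined.** The endpoint is anchored to implant, not to drug start, and SAP 2.2.1 also requires histology and/or clinical symptoms. How brief treatment would change anti-HLA results is uncertain.

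**Conclusion.** The point holds as a gap in assessment timing. Under the protocol and SAP as written, a compliant site can record an on-drug sample as the immune-panel baseline, and the reference state can differ between subjects. The share of the collection window affected runs from 0% (basiliximab first on Day 1 with nothing earlier) to 100% (any agent started at Visit 2).

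The consequence is confounded within-subject and between-subject reading of MLR, LST and Diab-Q for an exploratory objective. It does not make those data uninterpretable. The effect on anti-HLA sensitization is uncertain and probably small. The C-peptide primary endpoint is not touched. The direction and size of the bias, and the number of subjects affected, cannot be derived from the documents.

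The conclusion assumes that no ordering rule exists in the unseen laboratory manual or in the individual implant plans. The change is worth making because it is cheap and the lost sample is irreplaceable.

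**What to change.** **Protocol 6.2 and 7.11.4.** Keep the Visit 2 to Visit 3 window and the qualification condition, and add: *and before the first dose of any study immunosuppressant*. Check that the laboratory manual agrees.

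**SAP 4.3 or 7.3.7.** Define immune-panel baseline as the last sample before that first dose. Record sample time relative to first dose. Flag in the listing any subject whose only pre-implant sample is later. State that post-implant panels are drawn on drug, so changes from this baseline combine drug and implant effects.

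**Cost.** One condition in two protocol sections and a short SAP definition, with no additional sample and no change to any dose or drug schedule. The practical burden is tighter scheduling: processing of the cellular samples must begin within 24 hours of collection, and the draw must now fit before dosing as well. Where drug starts at or soon after Visit 2, the panel will have to be taken while some eligibility checks are still open, so some panels may be run on subjects who are not then implanted.
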